#### 13.2.4 Gaps in knowledge

The Platelia *Aspergillus* EIA and the Fungitell Assay have each shown reassuring operating characteristics in adults making these biomarkers an attractive option for screening for IFI in children. More importantly, the 2 diagnostic tests afford the possibility of identifying an IFI days to weeks before the clinical diagnosis is made. However, it is not reasonable to extrapolate results from these adult studies to children. There is an absence of data regarding the operating characteristics of either biomarker in large homogeneous cohorts of children with leukemia.

Additionally, no data exist on either biomarker in a cohort of pediatric patients receiving antifungal prophylaxis. The use of prophylactic anti-fungal therapy will likely reduce the incidence of IFI or suppress actual IFI and thus potentially alter the predictive values of these biomarkers. As noted above, the use of prophylactic therapy will likely become standard of care and therefore it is imperative to define the operating characteristics of these biomarkers in such a population.

Lastly, it may be optimal to consider the results of each biomarker in combination as opposed to evaluating the impact of each study independently. **The simultaneous interpretation of both Platelia *Aspergillus* EIA and the Fungitell Assay for the identification of IFI in children has never been evaluated.** It is plausible that interpreting the 2 biomarkers in combination would improve the sensitivity of detecting an IFI.

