### 13.3 Specific Aims

Primary Aim:

- i) To define the operating characteristics of 2 fungal antigen assays, Platelia *Aspergillus* EIA and Fungitell Assay for the identification of IA only and all IFI among pediatric AML patients receiving antifungal prophylaxis. This primary aim will have 3 sub-aims:
  - a) Define the test characteristics using a combination of the results from the Platelia *Aspergillus* EIA and Fungitell Assay for identifying IA only and all IFI.  
Hypothesis: A positive Platelia *Aspergillus* EIA **or** positive Fungitell Assay will be more sensitive at identifying patients with IA only or with IFI while on antifungal prophylaxis as compared to either test alone.
  - b) Define the test characteristics of the Fungitell Assay for identifying all IFI.  
Hypothesis: A single positive Fungitell Assay will have > 90% sensitivity in identifying all IFI in pediatric AML patients on antifungal prophylaxis.
  - c) Define the test characteristics of Platelia *Aspergillus* EIA for identifying IA only.  
Hypothesis: A single positive Platelia *Aspergillus* EIA will have > 90% sensitivity in identifying IA only in pediatric AML patients on antifungal prophylaxis.

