### 13.8 Statistical Design

#### 13.8.1 Sample Size and Estimated Event Rates

The parent trial comparing prophylaxis with caspofungin to fluconazole in newly diagnosed AML patients anticipates enrollment of at least 275 patients for each arm with a total cohort of approximately 550 patients. As noted above we anticipate that at least 80% of the patients enrolled in the parent trial will also be enrolled in this ancillary study. This will result in 220 patients from each study arm. Consent for testing will be included as a part of the parent trial enrollment, thus significantly limiting the need for additional resources to complete this biomarker study.

The estimated number of probable or proven IFI events for final analyses will be different for both proposed biomarkers as they account for different types of fungal infections and the incidence for each will vary by study arm. The Fungitell Assay has the potential to identify most pathogenic fungi and thus a majority of the probable or proven IFIs will be considered as true events (excluding IFIs from *Zygomycetes* and *Cryptococci*). The Platelia *Aspergillus* EIA is specific for *Aspergillus* and thus only probable or proven IA will be considered as true events for that analysis.

Based on Section 9.3.3 of the parent trial the estimated incidence of IFI for patients in the fluconazole group is 8% and 2% in the caspofungin arm. Assuming the enrollment of 220 patients in each study arm, there would 18 IFI events in the fluconazole group and 4 IFI events in the caspofungin group. Based on data from the CCG 2961 AML trial, one-third of microbiologically proven fungal infection were the result of *Aspergillus*. Therefore, it is estimated that 6 of the 18 IFI events in the fluconazole group will be IA and between 1 and 2 of the IFI events in the caspofungin group will be IA.

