#### 13.8.2 Sensitivity, Specificity, PPV, and NPV

The validity of a biomarker is based on whether the study appropriately categorizes patients with and without the illness in question (sensitivity and specificity). Alternatively the validity of a test can be measured by how well the test results predict the presence or absence of the disease (PPV and NPV). Collectively, sensitivity, specificity, PPV, and NPV are often referred to as the test's operating characteristics with the sensitivity and NPV being the most clinically relevant parameters for this study. Each component of the operating characteristics will be calculated based first on the entire cohort. As indicated in the sample size estimates above the incidence of IFI will vary between the two study arms. It is well documented that variations in the incidence/prevalence of a disease will impact the operating characteristics of a diagnostic test specifically for the PPV and NPV. Therefore, each assay's sensitivity, specificity, PPV and NPV will also be calculated separately for each study arm.

The operating characteristics for both the Platelia *Aspergillus* EIA and the Fungitell Assay will be computed at the patient level for each of the sub-aims as follows:

- a) Outcome of IA only **or** all IFI defined as a single positive test for either the Platelia *Aspergillus* EIA **or** the Fungitell Assay as compared to the EORTC/MSG criteria for proven or probable IA only **or** all IFI.
- b) Outcome of IA only defined as a single positive test for Platelia *Aspergillus* EIA only as compared to the EORTC/MSG criteria for proven or probable IA only.
- c) Outcome of all IFI defined as a single positive test for the Fungitell Assay as compared to the EORTC/MSG criteria for all proven or probable IFI.

Sensitivity, specificity, PPV and NPV and their accompanying 95% confidence intervals will be calculated using STATA statistical software version 11.0 (College Station, TX). As noted above, these parameters will first be calculated for the entire cohort and then for each study arm separately. The latter analyses are important as the incidence of IFI may vary by study arm thus impacting the interpretation of the assay results. A patient with multiple episodes of IFI will only be included in the analyses as a single IFI.

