#### 13.8.4 Sensitivity Analysis

Sensitivity analyses will be explored for reasoning expressed in both Sections 13.1 and 13.7 above. The first sensitivity analysis will attempt to identify the direction and magnitude of the bias resulting from the availability of clinical BG and GM testing outside of the ancillary study. Such testing has the potential to change the treating clinician's approach for diagnosing an IFI. It is possible that these test results could result in more or less investigation (i.e., radiologic imaging) to identify an IFI which could ultimately impact on the incidence of identified IFI. Therefore, in addition to calculating the operating characteristics for all patients enrolled as described in Section 13.8.2 above, the same operating characteristics will be calculated after excluding all patients that had at least 1 biomarker test result available to the treating clinician.

The second sensitivity analysis will be performed to explore the impact of the various factors described in Section 13.7 that may contribute to a positive result for either biomarker. False positive results would impact the final interpretation of sensitivity and PPV for each of the assays. However, it is also possible that one of the factors listed in Table 3 is present in a patient that truly has an IFI. Therefore, we plan to still include all patients in the primary analysis for calculation of each assays' operating characteristics. In this sensitivity analysis, we will eliminate all patients with a positive test that correlates in time with at least 1 of the factors listed in Table 3.

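### Section 13.8.2 does not tie a positive assay to the infection date, so an unrelated earlier-course positive can count as a true positive, which raises sensitivity or leaves it unchanged

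*Combined protocol and SAP*

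**What the plan says.** Section 13.8.2 states that the operating characteristics "will be computed at the patient level for each of the sub-aims as follows". The BG comparison is "Outcome of all IFI defined as a single positive test for the Fungitell Assay as compared to the EORTC/MSG criteria" for proven or probable IFI. The GM comparison (IA only) and the either-test comparison also rest on one positive result. Repeat infections are collapsed: "A patient with multiple episodes of IFI will only be included in the analyses as a single IFI". The same section ranks the parameters, "with the sensitivity and NPV being the most clinically relevant parameters for this study".

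Section 13.3 sets a hypothesis for each assay; for BG it is "A single positive Fungitell Assay will have > 90% sensitivity in identifying all IFI in pediatric AML patients on antifungal prophylaxis". It also expects the either-test rule to be more sensitive than either assay alone. Section 13.8.1 gives the expected numbers as "there would 18 IFI events in the fluconazole group and 4 IFI events in the caspofungin group", with 6 and 1 to 2 of these being IA.

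Table 2 in Section 13.4 plans 6, 5, 5 and 8 samples per patient in Courses I to IV. Section 13.2.4 gives the attraction of the assays: "the 2 diagnostic tests afford the possibility of identifying an IFI days to weeks before the clinical diagnosis is made".

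The one timing rule for a positive test is in Section 13.8.4, where a sensitivity analysis will "eliminate all patients with a positive test that correlates in time with at least 1 of the factors listed in Table 3". It concerns causes of false positives, not the infection.

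**The concern.** A positive in Course I and an infection in Course III make a true positive under this rule, even if every sample around the infection was negative. Retesting of positives (13.1.6), the ROC and consecutive-positive analyses (13.8.3) and the exclusions in 13.8.4 do not relate a positive to the infection date. The temporal wording in Appendix II concerns host factors and clinical criteria, not the research assays.

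Positives that meet a time link are a subset of any-time positives, so among infected patients the bias has one direction. It falls on a parameter the plan calls most relevant, in a study whose appeal is early warning. With so few infections, one credited patient visibly moves the point estimate.

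**Working it through.** **The plan's own figures.** Events: 220 × 0.08 = 17.6 (18) and 220 × 0.02 = 4.4 (4), total 22. Table 2: 440×6 + 380×5 + 337×5 + 216×8 = 2640 + 1900 + 1685 + 1728 = 7953. Both reproduce.

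**Inputs.** From Section 13.2.3.1: adult BG sensitivity/specificity 100%/90% in one study and 97.4%/28.6% in a second, which counted possible IFI as cases; adult GM 72.9%/94.7%. Assumptions: specificity applies per course, courses are independent, the two assays are independent, and infections are spread over the Table 2 slots. The documents give no repeat-test correlation.

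**Chance that a missed case is credited from an earlier course.** Slot weights are w = 0.332, 0.239, 0.212, 0.217, so 66.8% of slots fall after Course I. With q = 1 − specificity, credit = Σ w_k × [1 − (1 − q)^(k−1)].

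| Rule | q | Credit | If half of infections fall in Course I |
|---|---|---|---|
| BG | 0.10 | 0.123 | 0.092 |
| GM | 0.053 | 0.067 | 0.050 |
| Either | 1 − 0.90 × 0.947 = 0.148 | 0.176 | 0.132 |

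For BG: 0.239 × 0.10 + 0.212 × 0.19 + 0.217 × 0.271 = 0.123.

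**Gain over a same-course rule** = (1 − S) × credit, where S is true sensitivity.

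- Paired adult rates: BG 100/90, 0 points. BG 97.4/28.6, credit 0.577, so 0.026 × 0.577 = 1.5 points (ceiling 2.6). GM, 0.271 × 0.067 = 1.8 points.
- BG at 90% specificity with S assumed: S = 0.90 gives 0.912 (1.2 points); 0.70 gives 0.737 (3.7); 0.50 gives 0.562 (6.2).
- If false positives fully persist within patients, the gain is near 0.

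**Effect of one credited patient.** IFI: 1/22 = 4.5 points, for example 19/22 = 86% (exact 95% CI 65 to 97%) becoming 20/22 = 91% (71 to 99%). IA: 1/8 = 12.5 or 1/7 = 14.3 points.

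**What a window removes.** Take a BG assay with no information and a per-test positive rate of 1 − 0.90^(1/6) = 0.0174. Average 1 − (1 − 0.0174)^m over the slots, where m is the number of eligible samples up to the infection. Any time: 16.6%. Last 8 samples (28 days): 10.6%. Last 6 samples (21 days): 8.6%. No course has more than 8 planned samples, so also allowing all same-course samples leaves the 28-day figure unchanged. The window figures are upper bounds, because gaps between neutropenic periods leave fewer samples in a window.

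**The case against.** Four points deserve weight.

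- **Size.** A reader might infer a gain of 1 to 6 points at the cited adult rates. The documents do not support that: the upper values need true BG sensitivities of 70% or 50%, which appear nowhere in them. The paired adult rates give 0 to 2 points. The 90% BG specificity also comes from a study that used a cutoff above 60 pg/mL (Section 13.6.1.1), whereas the trial uses 80 pg/mL or more. Against that, the same section reports 15% of healthy children at or above 80 pg/mL, and Section 13.2.4 declines to extrapolate adult results to children. Independence between courses is doubtful too, since some Table 3 exposures are likely to recur.
- **Existing analyses.** Requiring two consecutive positives would cut earlier-course chance credit for BG from about 12% to about 0.2% under independence: 5, 9 or 13 earlier within-course pairs × 0.0174², weighted as above. Clustered false positives would raise this. The Table 3 exclusion also removes some unrelated positives. Both help, but the first changes the definition of a positive test and neither asks whether the positive belongs to the infection.
- **No decision at 90%.** Section 13.8.2 plans estimates with 95% intervals and no success rule. Both intervals shown for 19/22 and 20/22 contain 90%. A reader might infer that one credited case decides the hypothesis; it moves only the point estimate.
- **Patient-level scoring is deliberate.** Section 13.6.1.1 accepts lower specificity in return for sensitivity. A reader might infer that falling specificity over repeated courses is a further error; the stated trade-off makes it a reporting matter.

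**Conclusion.** The concern holds at modest size. As written, Section 13.8.2 credits positives unrelated to the infection, and the resulting bias in sensitivity is upward or nil. The best-supported range is 0 to 2 points. About 4 to 6 points for BG requires assumed sensitivities of 70% to 50%, and persistent false positives shrink the gain towards 0. All these sizes rest on adult specificities applied per course.

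Confidence intervals will be wide in any case, participation is optional and results are withheld from treating physicians (13.1.8). The change is still worth making: the rule biases a parameter the plan ranks highest, and choosing a window after results are seen would be hard to defend when one patient is worth 4.5 points for IFI or about 13 for IA.

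**What to change.** In Section 13.8.2, before assay results are linked to outcomes, prespecify a time-linked analysis:

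- A positive counts as true only if drawn on or before the date of first IFI (or IA) used for the time-to-IFI (or time-to-IA) endpoint, and either in the same neutropenic course or within a stated window before that date. An example is 28 days, with 21 days as a sensitivity analysis. Both exceed the cited median leads of 17 days (GM) and 10 and 5 days (BG).
- Later samples are excluded.
- The result is reported beside the any-time patient-level result.
- The text says that the window reduces chance credit without removing it: about 17% to 11% for an uninformative BG assay at 28 days.

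The cost is SAP wording and modest extra analysis. Samples are labelled with their date (13.1.2), and Section 9.3.1 already needs an event date. Sections 9.3.2 and 10.2 describe the committee as classifying cases, not dating them, so the text should say whose date is used.

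There are two downsides. Reported sensitivity may be slightly lower, and true signals earlier than the window drop out of the linked analysis, which is why the any-time result stays. A course-level specificity analysis would be useful optional reporting, not a correction.

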#### 13.8.3 Receiver Operator Characteristics Curve

In addition to understanding the operating characteristics of a diagnostic test at a single defined threshold, it is also important to understand how variations in the test's threshold can alter the test's operating characteristics. The receiver operating characteristics (ROC) curve is a useful approach to illustrate how these operating characteristics will change as the threshold changes. Therefore, a receiver-operating-

characteristics (ROC) curve will be generated with a series of sensitivities and specificities derived from various cutoff values. For the Platelia *Aspergillus* EIA cutoffs of > 0.5, 1.0, 1.5 and 2.0 will be used. For the Fungitell Assay cutoffs of  $\geq 40$ ,  $\geq 60$ ,  $\geq 80$ , and  $\geq 100$  pg/mL will be used to create the ROC. The ROC curve will be displayed graphically (sensitivity vs. 1-specificity) and evaluated numerically (c-statistic). The c-statistic (also referred to as the area under the curve (AUC)) varies from 0.5 to 1.0 and is a measure of the test's ability to discriminate between patients with and without the gold standard diagnosis. A c-statistic of 0.5 is possible by chance alone while a perfectly discriminating test will result in a c-statistic of 1.0.

Additionally, the ROC curves will be used in an exploratory analysis to identify the threshold for each biomarker assay that optimizes the diagnostic test's sensitivity while maintaining a reasonable specificity. The identified thresholds will be used to categorize each patient as "likely to have IFI or IA" and "not likely to have IFI or IA". Once these 2 sub-groups are defined we will calculate the incidence rates of IFI or IA for each sub-group and compare them. Because the anticipated incidence for IFI and IA may be variable between the two study arms (those receiving fluconazole and those receiving caspofungin) this approach will have to be done at the level of each study arm. The incidence rates will be compared statistically using Pearson's Chi-square analysis.

Finally, to further explore the ideal utility and interpretation of each biomarker, serial testing results will be explored. For this analysis the Platelia *Aspergillus* EIA will be considered positive when a patient has 2 consecutive tests > 0.5 GM index and the Fungitell Assay will be considered positive when a patient has 2 consecutive test results  $\geq 80$  pg/mL. Operating characteristics and ROC curves will be constructed in a similar manner as discussed above.

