### 13.1.8 Galactomannan and Beta-D glucan Assays

Testing will be performed by technicians blinded to each patient's clinical information. **Test results will not be made available to treating physicians since the utility of these tests is not yet established in children and because we will not be conducting testing in real time. Thus, results will not be utilized for clinical decision-making.**

To our knowledge BG testing is not routinely performed at many pediatric centers but may be performed at some of the COG sites while GM testing is currently performed at a number of pediatric centers. Regardless of the number of institutions offering such testing options, we anticipate that such testing will be ordered by a subset of treating physicians. The local BG and GM results will not be included in our final analysis of the 2 biomarker assays' operating characteristics. However, these results may effect a change from fungal prophylaxis to preemptive or empiric therapy and may encourage or discourage more comprehensive efforts to diagnose a proven or probable IFI in any given patient. This in turn may falsely influence our evaluation of the 2 biomarker assays' operating characteristics. For each patient we will identify whether local BG or GM testing has been performed and, via a sensitivity analysis, explore whether such a practice influences the operating characteristics. The plans for this sensitivity analysis are described in more detail in Section 13.8.4 below.

The Platelia *Aspergillus* EIA study is reported as a GM index. We will use the FDA-approved threshold of  $\geq 0.5$  GM index on a single test sample as our criteria for a positive test result. The Fungitell Assay is reported in pg per mL of patient's serum. The manufacturer recommendation for a single positive Fungitell assay result of  $\geq 80$  pg/mL will be used to define a positive test.

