#### 13.6.1 Justification of Methodologic Choices

##### 13.6.1.1 Justification for Chosen Thresholds for Platelia *Aspergillus* EIA and Fungitell Assay

IFI outcomes are often devastating, thus it would be desirable to optimize sensitivity at the potential expense of specificity. Furthermore, a highly sensitive test will likely result in a high negative predictive value. Clinicians caring for patients with positive tests would then have a heightened concern for IFI while a negative test result would reassure them that no further modifications to antifungal therapy are necessary at that time. It was with these intentions that the following threshold values were chosen to conclude negative and positive results for each biomarker.

The level of  $\geq 0.5$  GM index for Platelia *Aspergillus* EIA will be the established threshold to determine a positive result. This is the level that was established for FDA approval during testing in adults. The operating characteristics of this test have been evaluated in pediatric and adult patients using various cutoffs ranging from 0.5 to 1.5 as well as using single and consecutive positive results. Increasing the threshold level and requiring multiple consecutive positive results often reduced the sensitivity while optimizing specificity. As noted above, our goal is to optimize sensitivity and negative predictive value, at the risk of lower specificity and positive predictive value. Therefore, the lower threshold of  $\geq 0.5$  on a single test was chosen.

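### Section 13.8.3 builds each biomarker ROC curve from four preset cutoffs, which is expected to understate the AUC; for galactomannan, none lies below the positivity threshold

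*Combined protocol and SAP*

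**What the plan says.** Section 13.1.6 has the laboratory report a GM index and a beta-D glucan level in pg/mL, so both results are quantitative. Section 13.1.8 calls GM positive at an index of at least 0.5 "on a single test sample as our criteria for a positive test result", and Fungitell positive at 80 pg/mL or more.

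Under Section 13.8.3 the ROC curve "will be generated with a series of sensitivities and specificities derived from various cutoff values". The values are then listed. For GM, "cutoffs of > 0.5, 1.0, 1.5 and 2.0 will be used". For Fungitell, cutoffs of at least 40, 60, 80 and 100 pg/mL "will be used to create the ROC". The same curve is both plotted and summarised by a c-statistic, with no calculation method named. An exploratory analysis then uses it to "identify the threshold for each biomarker assay that optimizes the diagnostic test's sensitivity while maintaining a reasonable specificity". The section closes with a serial-testing analysis (two consecutive positives, again with GM above 0.5) whose curves are built in the same way.

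On priorities, Section 13.6.1.1 states that "our goal is to optimize sensitivity and negative predictive value, at the risk of lower specificity and positive predictive value". It reports that a higher GM threshold and a requirement for "multiple consecutive positive results often reduced the sensitivity while optimizing specificity". Its planned post hoc look at other cutoffs refers forward to the statistical section, so no finer curve is specified elsewhere.

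**The concern.** Three features of the construction do not fit its purpose.

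- **Area.** A trapezoid through four points must be closed by straight lines to (0,0) and (1,1). Where the true curve is concave these lines lie beneath it, so the area is too small. The long final segment, from the lowest cutoff to (1,1), matters most.
- **Range of the GM grid.** The lowest GM point is the positivity threshold, while the stated aim is to favour sensitivity.
- **Inequality.** The GM grid is strictly above 0.5 and the positivity rule is at least 0.5, so the first ROC point need not coincide with the main operating point. Only values exactly at 0.5 are affected.

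Sections 13.2.5 and 13.9 intend these results to inform use of the assays in later trials. An understated AUC, by an amount that differs between the assays, would make both the level and the comparison hard to interpret.

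**Working it through.** **The plan's event counts (Section 13.8.1).** 550 × 0.80 = 440 patients, 220 per arm. IFI: 220 × 0.08 = 17.6, stated as 18; 220 × 0.02 = 4.4, stated as 4. One third of these are invasive aspergillosis (IA): 18/3 = 6 and 4/3 = 1.3, stated as 1 to 2. The counts reproduce. The plan states no target AUC or precision.

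**GM search range (no model needed).** Sensitivity cannot rise as a cutoff rises. The smallest GM cutoff on the grid is 0.5, so the highest sensitivity on the grid is the one at 0.5. The Fungitell grid includes 40 and 60, below its threshold of 80, so it can reach higher sensitivity.

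**AUC model (assumed, not in the documents).** Log-normal assay values; non-case log-SD 0.5, 0.8 or 1.2; ratio of case to non-case SD 1 or 1.5 for GM, 0.7 or 1 for Fungitell. The four-cutoff AUC is the trapezoid through the listed cutoffs plus (0,0) and (1,1).

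**One GM case in full.** Take 72.9%/94.7% at 0.5, with log-SD 0.8 in both groups.

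- Full AUC = Φ[(z(0.729) + z(0.947))/√2] = Φ[(0.610 + 1.616)/1.414] = Φ(1.574) = 0.942.
- Points (1 − specificity, sensitivity) at 2.0, 1.5, 1.0 and 0.5: (0.0004, 0.131), (0.0014, 0.223), (0.0065, 0.399), (0.053, 0.729).
- Segment from 0.5 to (1,1): (1 − 0.053) × (0.729 + 1)/2 = 0.819.
- Segment from 1.0 to 0.5: (0.053 − 0.0065) × (0.399 + 0.729)/2 = 0.026. The remaining three sum to 0.002.
- Four-cutoff AUC = 0.847, a loss of about 0.10.

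**GM over the assumed SDs.**

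| Operating point | Full AUC | Four-cutoff AUC | Loss |
|---|---|---|---|
| 72.9%/94.7% at 0.5 | 0.920-0.942 | 0.843-0.851 | 0.07-0.10 |
| 72.9%/94.7% at 1.0 | 0.920-0.942 | 0.888-0.920 | 0.02-0.04 |
| 72.9%/94.7% at 1.5 | 0.920-0.942 | 0.897-0.929 | 0.01-0.02 |
| 90%/90% at 0.5 (assumed) | 0.962-0.965 | 0.921-0.935 | 0.03-0.04 |
| 99%/90% at 0.5 (assumed) | 0.995-0.996 | 0.985-0.992 | at most 0.01 |

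The first three rows differ because Section 13.2.3.1 gives the adult figures without an index cutoff. In the first row, adding cutoffs from 0.1 to 0.4 brings the AUC back to 0.912-0.936, so the missing low end causes most of the loss.

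**Fungitell.** Section 13.6.1.1 gives 22% of healthy children above 60 pg/mL and 15% at 80 or more. The non-case log-SD is then ln(80/60)/[z(0.85) − z(0.78)] = 0.288/0.264 = 1.09. With assumed sensitivities at 80 pg/mL of 60%, 80%, 90% and 95%, the loss is 0.02-0.04; for example, at 90% with equal SDs, 0.949 becomes 0.913. Healthy-child values are only a stand-in for peak values in this population.

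**Small-sample check.** 10,000 simulated data sets, 7 IA cases and 433 non-cases, log-SD 0.8.

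| Operating point at 0.5 | All values: mean (SD) | Four cutoffs: mean (SD) | Four-cutoff AUC no higher |
|---|---|---|---|
| 72.9%/94.7% | 0.942 (0.041) | 0.846 (0.086) | 96% |
| 90%/90% | 0.965 (0.030) | 0.928 (0.062) | 90% |

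**The case against.** **The method is not stated.** Section 13.8.3 does not say that the c-statistic is trapezoidal. A fitted smooth curve or continuous values would avoid the loss. This stands, and the conclusion is conditional on it; the trapezoid is the ordinary reading of a curve made from listed cutoffs.

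**The size is uncertain.** A reader might take a loss near 0.10 as the documents' own implication. They do not support that. It needs the adult figures to apply at 0.5. Section 13.6.1.1 ties 0.5 to the adult approval testing but also says that studies used cutoffs from 0.5 to 1.5. Three of the four paediatric studies in Table 1 (Section 13.2.3.2) show 100% sensitivity, where the loss is negligible, although that section says they cannot be extrapolated to patients on prophylaxis. The range stands, not its top.

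**The upward GM grid has a rationale.** The threshold was set at the low end of the studied range to favour sensitivity, and the search also asks for reasonable specificity, so higher cutoffs show what specificity could be gained. That justifies keeping those points, not omitting lower ones. A search below 0.5 on so few IA cases does risk overfitting, and the fix must guard against that.

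**The stakes are limited.** The study is optional, the threshold search is labelled exploratory, and results are withheld from treating physicians. This also stands.

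**Conclusion.** The point holds in a limited form. With a trapezoidal c-statistic, four cutoffs are expected to understate the AUC: for GM by anything from 0.01 or less up to 0.10, depending on sensitivity at 0.5 and on the cutoff behind the adult figures; for Fungitell by 0.02-0.04. These sizes rest on the log-normal model and the assumed operating points. In a single small data set the sign can occasionally reverse. The four-point AUC is also about twice as variable in the simulation, while the GM AUC stays imprecise under either method with 7 to 8 expected IA cases.

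That the GM search cannot improve on sensitivity at 0.5 follows from the grid alone. A reader might extend this to both assays, but the Fungitell cutoffs of 40 and 60 rule that out. Nor does the point reach the trial's primary comparison or the operating characteristics at fixed thresholds in Section 13.8.2.

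**What to change.** In Section 13.8.3:

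1. Compute the empirical ROC curve and the nonparametric AUC with a 95% CI from each patient's peak GM index and peak beta-D glucan value. A patient has at least one result at or above a cutoff exactly when the peak is, so this matches the patient-level single-positive rule in Section 13.8.2.
2. Keep the listed cutoffs as labelled points on the curve.
3. Write the GM cutoff as at least 0.5, here and in the serial-testing paragraph, to agree with Sections 13.1.8 and 13.6.1.1.
4. Show GM points below 0.5.
5. Report any threshold chosen from the data as exploratory, with CIs for its sensitivity and specificity, and state that only about 6 and 1-2 IA cases are expected in the two arms.

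The cost is SAP wording. The quantitative results are already reported under Section 13.1.6, so no extra samples or assays are needed.
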